GLOSSARY OF TERM

ADR	Adverse Drug Reaction
AE	Adverse Event
CBC	Complete Blood Count
CKD	Chronic Kidney Disease
CI	Confidence Interval
CRO	Contract Research Organization
CSR	Clinical Study Report
CRF	Case Report Form
EMA	European Medicines Agency
EPO	Erythropoietin
GCP	Good Clinical Practice
IC	Informed Consent
ICH	International Council for Harmonisation
IEC	Independent Ethics Committee
ITT	Intent-To-Treat
IWRS	Interactive Web Response System
NAb	Neutralizing Antibody
PP	Per-protocol
SAE	Serious Adverse Event
SAP	Statistical Analysis Plan
SBP	Similar Biotherapeutic Product
SOC	System Organ Class
WHO	World Health Organization

PROTOCOL SYNOPSIS

Study title	The Clinical Study for Evaluating the Safety and Efficacy Of Epodion® During Maintenance Period Until Evaluation Period On CKD (Chronic Kidney Disease) Patients: An Open Label, Randomized, Active Drug-Comparative, Parallel-Designed, Multi- Center Clinical Study
Sponsor	Daewoong Pharmaceutical Co., Ltd.
CRO	PT. Equilab International
Institution and Principal Investigator	Gatot Soebroto Army Hospital Internal Medicine Department, [name]
Study Period	Total 36 - 40 weeks 
 • Screening period (-4) weeks • Titration period 4~8 weeks • Baseline evaluation period 4 weeks • Maintenance period 24 weeks • Evaluation Period 4 weeks
Study Population	Anemia Associated with Chronic Kidney Disease aged ≥ 18 years and undergoing hemodialysis in hospital site
Objectives	To evaluate the safety and efficacy of Epodion® on Chronic Kidney Disease (CKD) patients
Study Phase and Design	An Open Label, Randomized, Active Drug-Comparative, Parallel-Designed, Multi-Center Clinical Study, Phase IV Study
Method	
This clinical study was designed as an open label, randomized, active-drug comparator, parallel designed, and multicenter study in hemodialysis patients with anemia.
 
Once subjects voluntarily consented to participate in the clinical study, medical examinations and tests required in the protocol will be conducted, eligibility of each subject will be checked, and only subjects who meet all of the screening criteria will be proceeded for first phase of study which is titration period.
 
In Titration period (4 ~ 8 weeks), all eligible subjects will be administered with Eprex® at individualized dose. Routine hematological (Complete Blood Count, CBC) test will be performed every two weeks to monitor Hb level as consideration for dose adjustment. Eprex® doses should be

	
closely titrated to achieve target Hb range 10-12 g/dL. Subject who meets the target range at week 4 will be allowed to skip the remaining 4 weeks of titration period and continue to Baseline Evaluation Period.
 
During the 4 weeks of Baseline Evaluation Period, laboratory tests required in the protocol are performed every two weeks and recorded as baseline data.
 
Subjects who meet the inclusion criteria, none of the exclusion, and achieve baseline evaluation target criteria will be randomized into either test group (Epodion® treatment) or control group (Eprex® treatment).
 
In Maintenance period, the administration dose of Eprex® and Epodion® is equal to the previous dose in titration period. Dose is allowed to be increased or decreased during maintenance period at an appropriate level to maintain Hb level 10-12 g/dL according to condition of subjects. During maintenance period, blood samples will be collected every two weeks for routine hematological test to monitor the efficacy and as consideration for dose adjustment.
 
In the Evaluation period, blood samples will be collected every two weeks. The mean of Hb change, weekly dosage, and hematocrit between baseline and evaluation period will be evaluated as efficacy assessment.
								
Investigational Product	
Treatment: Recombinant Human Erythropoietin Alfa, Epodion® (Daewoong Infion)
 
Reference: Recombinant Human Erythropoietin Alpha, Eprex® (Janssen)
								
Dosage & Administration, and Route of Administration	
Initial Epoetin dose administered according to previous dose. In Maintenance period, Epoetin dose may be increased or decreased at an appropriate level according to the condition of the subjects.
								
Number of subjects	
  
 	Study Group (Epodion®)	Control Group (Eprex®)	Total Sample Size	
   
 Evaluated Case	50	50	100	
  
		Study Group (Epodion®)	Control Group (Eprex®)	Total Sample Size	Evaluated Case	50	50	100
	Study Group (Epodion®)	Control Group (Eprex®)	Total Sample Size						
Evaluated Case	50	50	100						
	
Inclusion Criteria:
 
a. Male or female patients who are at least 18 years old and younger than 75 years of age at the time of screening visit.
								


Screening Criteria:
	
b. Patients with End-Stage Renal Failure (ESRD) who are chronically receiving hemodialysis and have anemia.c. Patients with a mean baseline Hb concentration within Hb level ≥ 9 g/dL during the screening period.d. Haemodialysis patients with anemia associated with Chronic Kidney Disease (CKD) currently receiving stable maintenancetherapy with Epoetin alfa at least once per week.e. Adequate iron substitution status (serum ferritin ≥ 100 $\mu\text{g} / \text{L}$ (100ng / mL) or saturated transferrin levels $\geq 20\%$).f. Patients who understand the information provided to them or their representatives and may provide written consent. 
Exclusion Criteria:
 
a. Contraindication with Epoetin therapy.b. Documented active bleeding in the last 12 weeks prior to screening period.c. Any blood transfusion within the last 2 weeks prior Screening period.d. History of malignancy of any organ system within the last 5 years.e. Patients with uncontrolled hypertension (in case the mean value of diastolic blood pressure as measured 4 times during the baseline observation period is 110 mmHg or more).f. Patients hyporesponsive epoetin treatment or had medical history of experiencing pure red blood cell forming failure after being administered with Epoetin products.g. Known bone marrow fibrosis (osteitis fibrosa cystica).h. Patient with serious cardiovascular disorders: myocardial infarction, patients with congestive heart failure (NYHA class III or higher), ischemic vascular disease.i. Patient received percutaneous coronary intervention (PCI),
----------------------------	---

	
or coronary artery bypass grafting (CABG) during the last 6 months prior to screening.
 
j. Patients with ALT or AST exceeding the upper limits of the normal level by more than 5-folds.
 
k. Patients whose kidney transplant is expected or already planned for survival.
 
l. Secondary anemia to other causes different to the CKD (aplastic anemia, hemolytic anemia, sickle cell anemia, multiple myeloma, leukemia, myelodysplastic syndrome).
 
m. Patients with the following diseases and who are considered unfit to enroll in the clinical study: mental system disease, mental disease, drug intoxication, epilepsy, lung infarction, cerebral infarction, positive HIV antibody, systemic lupus erythematosus, immunosuppressive condition and general infection.
 
n. Pregnancy or lactation period in female patients, or women of childbearing potential without an effective method of birth control.
 
o. Patients who were considered unfit for study by the principal investigators or by the co-investigator.

Baseline Evaluation Period Criteria
	
Subject who voluntarily consented to participate in the clinical study, meet eligible criteria, stable with Eprex®, will be evaluated again to assess the subject eligibility prior randomization and maintenance period. Only subjects who meet eligible baseline criteria will continue to randomization and maintenance period.
 
Inclusion criteria:
 
a. Subject achieved Hb target 10-12 g/dl.
 
b. Adequate iron substitution status (serum ferritin \geq 100 μg / L (100 ng / mL) or saturated transferrin levels \geq 20%).
 
c. Patients who have gone through the baseline evaluation at the time of the screening visit or before randomization.
 
d. Patients with dry weight less than 5% during the baseline evaluation period.
 
e. Subject are reliable and will willingly cooperate during the maintenance period and observe the restrictions.

	
Exclusion Criteria:
 
 a. Any blood transfusion within the last 2 weeks prior to screening period. b. In case the EPO administration dose during the baseline evaluation period (week 9-12 / 13-16) is increased or decreased by 20% or more. c. Currently contraindicated with Epoetin therapy. d. Subject administered with prohibited drug (cyclosporine, androgen, and chemotherapy agents). e. Occurrence medical condition which can affect efficacy data during maintenance period judged by principal investigator or sub-investigator.

Outcome Measures:
	
Primary endpoint
 
 a. Mean change in Hb (hemoglobin) level between the baseline period and the evaluation period 
Secondary endpoint:
 
 b. Mean change in weekly dosage per kg body weight between the baseline period and the evaluation period. Instability rate of Hb (hemoglobin) level during maintenance and evaluation period as defined when Hb (hemoglobin) level dropped below 8 g/dL or increase more than 13 g/dL. c. Evaluation Hb (hemoglobin) and hematocrit level during maintenance and evaluation period.
	
Safety Evaluation:
 
Incidence adverse events.

Study flow
	
The diagram illustrates the study flow timeline. It begins with 'Informed consent' at -4 weeks, followed by a 'Screening' period. At Week 0, the 'Titration Period' (4/8 weeks) starts. At Week 4, the 'Baseline Evaluation' (4 weeks) begins. At Week 8, 'Randomization' occurs. The study then splits into two parallel paths: one for 'Epodior' and one for 'Eprex®'. Both groups enter a '24 weeks Maintenance Period' starting at Week 8. At Week 32, a '4 weeks Evaluation Period' begins for both groups. The study concludes at Week 36 for the Epodior group and Week 40 for the Eprex® group, marked as 'Study Completed'.

Study timeline
	

Procedure and Assessment	Screening	Titration Period			Baseline Period			Maintenance Period												Evaluation Period						
		0	2	4	6	8	10	12	10/14	12/16	14/18	16/20	18/22	20/24	22/26	24/28	26/30	28/32	30/34		32/36	34/38				
Week	-4																									
Informed consent form	■																									
Patient demography	■																									
Medical history	■																									
Prior Medication	■																									
Inclusion/exclusion criteria	■																									
Baseline Target Evaluation ¹⁾						■	■	■	■																	
Randomization ³⁾																										
Concomitant Medication																										
Eprex® administration ²⁾									Administer at an appropriate level for each subject																	
Epodion® administration ²⁾									Administer according to the existing baseline dosage																	
Lab Test	CBC (Hb)	■	■	■	■	■	■	■	■	■	■	■	■	■	■	■	■	■	■	■	■	■	■	■	■	
	CBC (Hct)	■							■	■	■	■	■	■	■	■	■	■	■	■	■	■	■	■	■	
	Iron status	■							■	■	■	■	■	■	■	■	■	■	■	■	■	■	■	■	■	
	HIV	■																								
Blood Chemistry (ALT&AST)		■																								
		■																								
Pregnancy Test	■																									
Safety Assessment ⁴⁾									Every time																	

1. Subject must achieve baseline target Hb level 10-12 g/dL prior enter maintenance period. If during 4-week titration period subject did not achieve baseline Hb level 10-12 g/dL, titration period will be extended maximum until week 8.
2. Doses must be individualized to ensure that hemoglobin is maintained at an appropriate level for each subject. In the screening period, initial dose is 50 IU/Kg body weight three times per week. During titration, dose id titrated closely to achieve baseline Hb level 10-12g/dL. In maintenance period administer Eprex® and Epodion® equal previous stable dose in titration period. Dose is allowed to be increased or decreased during maintenance period at an appropriate level according to the condition of the subjects.
3. Only the subjects within the inclusion/exclusion criteria and achieved baselinetarget evaluation criteria should be processed to randomization and maintenance period. When the subject achieves baseline target Hb level 10- 12 g/dL in 4 weeks titration period randomization will be done in week 8, if subject fail achieves Hb 10-12 g/dL in 4 weeks titration period, titration period will be extended until week 8. Subject will be screened failure and cannot enter maintenance period if during maximum 8 week titration cannot achievetarget baseline Hb level 10-12 g/dL.
4. Safety assessment will be evaluated based on comparison incidence of adverse event between Epodion® and Eprex®. Incidence of adverse eventswill be recorded during maintenance and evaluation period.

CHAPTER I. INTRODUCTION

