4.2 Safety Evaluation

Safety was evaluated based on incidence of adverse event.

Reported any symptoms from subject or other health care practitioner defined adverse event if appear after subject administered with investigational product (both Eprex® or Epodion®), and divided into local reactions and general reactions, and the details are as mentioned below:

- a. Local reaction: Pain, Tenderness, Erythema/Redness, Induration/Swelling
- b. Systemic reaction: Fever, Nausea/vomiting, Diarrhea, Headache, Fatigue, Myalgia.

Vital sign abnormalities are defined as adverse event if there are any clinical significance increase or decrease value including blood pressure, body temperature, heart rate, and respiratory rate after subject administered with investigational product (both Eprex® or Epodion®).

Laboratory test findings defined as adverse event if there are any clinical significance increase or decrease laboratory results including hematology test, blood chemistry test, and urinalysis after subject administered with investigational product (both Eprex® or Epodion®). If any findings after subject administered with investigational product disease temporary, finding abnormalities of electrocardiogram, X-ray, MRI also recorded as adverse event.

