4.4.4 Maintenance Period (Week 9-32/13-36)

During the maintenance period (Week 9-32/13-36), subjects who met the criteria were given Epoetin treatment according to the randomization allocation. Administration of Eprex® or Epodion® will be done with same doses regimen during titration period through intravenous injection. Epoetin dose may be increased or decreased at an appropriate level according to the condition of the subjects. Subject Hb levels were controlled to reach a range of 10-12 g/dL. Blood collection is carried out once every two weeks for the purposes of routine hematological test. Adverse event concomitant medication, and instability rate of Hb data is observed during the maintenance period. Concomitant medication during the study were recorded in the Case Report Form (CRF).

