4.4.5 Treatment Evaluation Period (Week 33-36/37-40)

The week 33-36/37-40 is the treatment evaluation period. Hemoglobin mean data, weekly Epoetin dose, and hematocrit will be compared with the baseline period as an efficacy evaluation parameter. Adverse events, concomitant medication, and instability rate of Hb data is observed during the maintenance period.

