6.2 Dosage, Administration, and Administration Period

The drug dose should be individualized, during titration period Eprex® doses should be closely titrated to achieve target Hb range 10-12 g/dl. During maintenance period, the administration dose of Eprex® and Epodion® is equal to the previous dose in titration period. Dose is allowed to be increased or decreased during maintenance period at an appropriate level to maintain Hb level 10-12 g/dl according to condition of subjects. Route of administration for this study is Intravenous injection (IV). Investigational product will be administered when subject enrolled until the end of the study.

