7.1 Definition of analysis group

7.1.1 Safety Set

The Safety Set will consist of all enrolled subjects who received at least 1 dose of the investigational product. In the case of dosing administration error, analyses on the Safety Set will be conducted according to actual treatment received.

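### The start point for recording adverse events is inconsistent, and the window in the study timeline footnote leaves 8 to 12 weeks of study Eprex before randomisation outside it

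*Protocol*

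**What the plan says.** **Recording window.** Footnote 4 to the study timeline (protocol synopsis) describes a comparison of adverse-event incidence between the two products and says that incidence will "be recorded during maintenance and evaluation period". Sections 4.4.2 (titration) and 4.4.3 (baseline evaluation) do not mention adverse events. Section 4.4.4 says "Adverse event concomitant medication, and instability rate of Hb data is observed during the maintenance period". Section 4.4.5, which covers the evaluation period, again names maintenance: "Adverse events, concomitant medication, and instability rate of Hb data is observed during the maintenance period".

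**What counts as an adverse event.** Protocol section 4.2 says that a reported symptom is "defined adverse event if appear after subject administered with investigational product (both Eprex® or Epodion", with no condition that it follow randomisation.

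**When study drug starts.** The synopsis lists Eprex under Investigational Product and gives it to all eligible subjects in titration. Section 6.2 says: "Investigational product will be administered when subject enrolled until the end of the study".

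**Documentation and reporting.** Section 8.2 requires any adverse event that is present to be assessed and entered in the CRF. Section 8.4 requires serious events in the study to be reported to the sponsor within 24 hours. Neither gives a start date.

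**Analysis.** Protocol section 7.1.1 and SAP section 1.1 say: "The Safety Set will consist of all enrolled subjects who received at least 1 dose of the investigational product". The Full Analysis Set is restricted to randomised subjects, but the Safety Set is not. Protocol section 7.5 and SAP section 3.3.1 tabulate treatment-emergent events by treatment group. Neither document defines treatment-emergent or its reference date.

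**The concern.** A site that follows footnote 4 and sections 4.4.2 to 4.4.5 has no instruction to log adverse events during titration and baseline evaluation. A site that follows sections 4.2 and 8.2 logs them. Sites may therefore collect different data under one protocol.

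Three things are at stake.

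1. **Non-serious run-in events.** Doses are titrated in this period. Subjects can leave because of side effects (section 5.3), or be excluded before randomisation for a new medical condition or contraindication (section 5.2, exclusions c and e). The non-serious events behind such exits could go unrecorded.
2. **Treatment emergence.** Without a systematic record of what was present at randomisation, deciding whether a later event is new, worse or merely continuing is a retrospective judgement. The trial is open label, so the person making that judgement knows the product.
3. **Denominator.** Subjects who take Eprex in the run-in but are never randomised may or may not belong to the Safety Set. If they do, they have no recording period under footnote 4 and no randomised arm to be tabulated under.

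**Working it through.** **Inputs** (protocol synopsis, Study Period): "Titration period 4~8 weeks", "Baseline evaluation period 4 weeks", maintenance 24 weeks, evaluation 4 weeks. Randomisation follows the baseline evaluation period (section 4.4.3; footnote 3). Eprex continues through baseline evaluation, since section 5.2 excludes subjects whose dose changes by 20% or more in that period.

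**Step 1. Reproduce the stated total.** Total = titration + baseline + maintenance + evaluation.
- Short titration: 4 + 4 + 24 + 4 = 36 weeks.
- Long titration: 8 + 4 + 24 + 4 = 40 weeks.

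This matches the stated 36 to 40 weeks, which therefore excludes the 4-week screening period.

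**Step 2. Time on study Eprex before randomisation.** 4 + 4 = 8 weeks, or 8 + 4 = 12 weeks.

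**Step 3. Share inside and outside the footnote 4 window.** The window is 24 + 4 = 28 weeks.
- Inside: 28/36 = 77.8%, or 28/40 = 70.0%.
- Outside: 8/36 = 22.2%, or 12/40 = 30.0%.
- Per 100 randomised subjects: 800 to 1,200 subject-weeks outside.

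These are shares of time on study drug, not of events. They apply to subjects who reach randomisation. A titration failure has at most 8 weeks of titration Eprex.

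**Step 4. Sensitivity to the dosing start.** Footnote 2 and section 4.4.6 place the initial dose in the screening period, while the synopsis Method and section 4.4.2 start study Eprex in titration. These places need reconciling. If dosing covered the 4 weeks of screening, the part outside would be 12/40 = 30.0% to 16/44 = 36.4%. The main figures do not use this reading.

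**Step 5. Apply the text to three cases.**

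| Case | Section 4.2 | Section 8.2 | Footnote 4 | Analysis |
|---|---|---|---|---|
| Non-serious headache in week 3 of titration | Adverse event | Enter in CRF | Outside window | No place for it specified |
| Same headache, still present after randomisation | Adverse event | Enter in CRF | Inside window once randomised | Treatment-emergent or not: undefined |
| Subject dosed with Eprex who fails titration | Events count | Enter in CRF | No recording period | In the Safety Set only if enrolled includes the run-in; no randomised arm |

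In each row the sections give different answers or leave one open.

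**Step 6. The meaning of enrolled.** Section 6.2, and the contrast with the randomised wording of the Full Analysis Set, suggest that enrolment precedes randomisation. The sample-size rationale in section 3.2 says about 100 subjects will be enrolled, and the synopsis splits 100 subjects 50/50 between the arms, which suggests that enrolled means randomised. Footnote 3 calls titration failures screen failures. The documents do not settle it.

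**The case against.** The strongest defence is that the protocol already covers the run-in. Footnote 4 does not say that recording is confined to its window. The sentence follows one about comparing the products, so it may only set the period for the comparative analysis. The Safety Assessment row it annotates is marked as applying every time, although the text available here does not show which columns that mark spans. Section 8.2 has no time limit, section 8.4 covers serious events throughout the study, and section 9.4 requires periodic reporting of adverse events to the sponsor. Section 6.4.1 records medication given for adverse events, and section 5.2 reassesses intercurrent conditions before randomisation. A post-randomisation window also suits both the between-arm comparison and the safety objective, which concerns use of Epodion.

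Much of this stands. An exclusive window is an inference, serious run-in events are reportable, and the post-randomisation window is the right one for comparing arms. But the general sections do not override the footnote; they add a second instruction that differs from it. Medication records and an eligibility check give some information on ongoing conditions, but they are not an adverse-event log with onset dates and severity.

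A reader might infer three stronger conclusions, which the documents do not support:

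- **That all run-in safety data are lost.** Section 8.4 keeps serious events reportable, so the exposure is mainly to non-serious events.
- **That the comparison is biased against Epodion.** Both arms have the same Eprex run-in, so a continuing event can be miscounted as new in either arm, and randomisation balances this in expectation.
- **That run-in failures dilute the adverse-event rates.** This requires one reading of an undefined word, a rule for tabulating subjects without an arm, and a failure rate. The documents supply none of these.

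**Conclusion.** The inconsistency is real and should be corrected. For subjects who reach randomisation, 22% (8 of 36 weeks) to 30% (12 of 40 weeks) of time on study drug lies outside the recording window in footnote 4, although the protocol's own definition makes events in that time adverse events. This rests on the stated period lengths, on study Eprex starting in titration, and on sites taking the footnote at its word.

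The consequence is limited but not trivial. Non-serious run-in events may go unrecorded, and treatment emergence has neither a definition nor a systematic baseline record. The randomised comparison is not biased by the window itself; the weakness is that attribution falls to retrospective, unblinded judgement in both arms. The Safety Set question is conditional: if enrolled includes run-in failures, they enter with no recording period and no randomised arm. The ambiguity needs resolving, but its numerical effect cannot be stated from the documents.

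**What to change.** 1. Amend footnote 4 and sections 4.4.2 to 4.4.5 so that adverse events and serious adverse events are recorded from the first study Eprex dose to the end of the evaluation period. Correct section 4.4.5 so that it names the evaluation period, and make sections 8.2 and 8.4 refer to the same start point.
2. List run-in events separately from post-randomisation events, including those in subjects who are never randomised.
3. In protocol section 7.5 and SAP section 3.3.1, define a treatment-emergent event as one that starts or worsens after the first randomised dose.
4. Define enrolled in protocol section 7.1.1 and SAP section 1.1, and use randomised and treated subjects as the denominator for between-arm safety tables.

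The cost is wording in the protocol and SAP and a few CRF pages for the run-in. No visits are added, because subjects already attend for dosing and a blood count every two weeks. If recruitment has begun, run-in events not captured so far cannot be reliably recovered, but items 2 to 4 can still be settled before database lock.
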